9.2.2 Dose Escalation Rules

Dose escalation will occur in accordance with the rules listed below.

- The DLT window is 28 days.
- A minimum of 3 patients will be initially enrolled per cohort.

- If 1 of the first 3 patients enrolled in a given cohort experiences a DLT, at least 3 additional patients will be enrolled in that cohort.
- If less than one-third of evaluable patients in a given cohort experiences a DLT (e.g., DLTs in 0 of 3 or \leq 1 of 6 patients), escalation will proceed to the next higher dose level.
- If a DLT is observed in one-third (e.g., 33%) or more of patients (e.g., 2 or more of up to 6 patients), the dose combination at which this occurs will be considered intolerable and the MTD will have been exceeded.
- The highest dose level at which 0 or 1 of 6 experience a DLT will be declared the MTD. If only 3 patients were initially evaluated at that dose level, an additional 3 patients will be enrolled to evaluate for DLTs at that dose level.
- After dosing has been completed in each cohort, safety and PK data (as applicable) will be reviewed by and dose escalations decisions made by the Sponsor, and investigators and study staff from all participating sites.
- If \geq 2 patients in one cohort experience \geq Grade 2 toxicities that are considered possibly or probably related to PLX9486, PLX9486 combined with PLX3397, or PLX9486 and sunitinib within the first 28 days, the study committee will determine the dose escalation increment after review of the safety, PK, and PD data.

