9.2.1 Dose Escalation

9.2.1.1 Part 1: Dose-escalation Cohorts

The initial dosing regimen of PLX9486 will be daily by oral administration. Each treatment cycle will be 28 days.

Cohorts of patients will be enrolled using the standard “3+3” design. The starting dose level of PLX9486 will be 250 mg/day (Cohort 1) using a once-daily (QD) dosing regimen. For higher total daily doses, a split dosing schedule (e.g., twice-daily [BID]) may be used at the current dose level under study or with previously studied daily dose levels. In the absence of Grade ≥ 2 toxicity that is considered “possibly” or “probably” related to the study agent or dose-limiting toxicity (DLT) and in conjunction with review of the PK data, dose escalation is planned to occur as indicated in [Table 16](#) and as stipulated below.

Table 16: PLX9486 Administration in Part 1: Initial and Potential Dose-escalation Cohorts

Cohort Number	PLX9486 Dose Level (mg/day) ^a	Number and Unit Strength
4	1000	20 × 50 mg
5	500 (BID)	10 × 50 mg (BID)
6	1500	30 × 50 mg
7	2000	40 × 50 mg

^a Dosing interval/frequency will be QD unless otherwise specified (e.g., BID dosing).

Further dose escalation or de-escalation may be considered depending upon safety and PK findings and discussion between the Sponsor and the investigators. Dose escalation will continue unless there are dose-limiting toxicities in ≥ 2 of at least 6 patients (i.e., 33%) in one cohort within the first 28 days.

Also, dose escalation and reduction in smaller increments may be undertaken at any time based upon emerging safety, PK, and PD data.

If a DLT is observed in one patient in the initial cohort of 3 patients, an additional 3 patients will be treated at that dose (see [Section 9.3](#)). If DLT is observed in 2 or more patients of either 3 or 6 patients (i.e., $\geq 33\%$ of patients treated) at a dose level, then a lower dose level of PLX9486 may be introduced unless no further reductions are feasible. If no DLT is observed, the recommended dose for further evaluation may be established based on toxicity, PK, and convenience of dosing in approximately 3 to 6 patients treated at that dose. Dose escalation will only be permitted if adequate safety and tolerability have been demonstrated at the previous lower dose for 28 days.

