9.2.1.2 Part 2: Extension Cohorts

[REDACTED]

Part 2b. Cohorts of patients will be enrolled using the standard “3+3” design. The PLX9486 dose escalation may follow the pattern established in Part 1, starting at $\leq 50\%$ of the MTD/RP2D established in Part 1. In the absence of Grade ≥ 2 toxicity that is considered “possibly” or “probably” related to the study agent and in conjunction with review of the pharmacokinetic data, dose escalation in Part 2b is planned to occur as indicated in [Table 17](#).

Table 17: PLX9486 and PLX3397 Administration in Part 2b: Initial and Potential Dose-escalation Cohorts

Cohort Number	PLX9486 Dose Level (mg/day) ^a	PLX3397 Dose Level (mg/day)
1	Approximately 50% of Part 1 RP2D	600 (200 mg in AM and 400 mg in PM)
2	Approximately 100% of Part 1 RP2D	600 (200 mg in AM and 400 mg in PM)
3	100% of Part 1 RP2D	400 mg QD (Cycles 1 and 2)
		600 mg QD (Cycle 3 +) ^b
4 +	TBD ^c	TBD ^c

RP2D = recommended phase 2 dose; TBD = to be determined

^a PLX9486 administered once-daily (QD) or for higher total daily doses, as split doses (e.g., twice-daily [BID]).

^b At the discretion of the investigator and in the absence of clinically significant drug-related toxicity ([Section 9.3](#)) during Cycles 1 and 2.

^c Based on a review of the data by the Study Committee.

Dose escalation will continue unless there are DLTs in ≥ 2 of 6 patients in one cohort within the first 28 days of continuous dosing.

[figure not shown]
Further dose escalation and reduction in smaller increments may be undertaken at any time based upon emerging safety, PK, and PD data. Dose adjustments may also include increasing the number of patients at a given dose level as a result of the review of safety and PK data by the Sponsor and investigators. In addition, alternative dosing schedules may be explored, such as continuous dosing followed by a rest period, staggered dosing of the agents, etc., depending on the safety, PK, or PD-generated data, as well as data from other ongoing PLX3397 studies.

If a DLT is observed in one patient at a given cohort, an additional 3 patients will be enrolled into the cohort. If DLT is observed in ≥ 2 of at least 6 patients (i.e., $\geq 33\%$) at a dose level, then a lower dose level of PLX9486 may be introduced to the combination regimen. If no DLT is

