9.2.4 Dose De-escalation for PLX9486 combinations

Combination with PLX3397: If ≥ 2 of the first 6 patients who receive the first dose level in Part 2b experience a protocol-defined DLT, the administration of PLX9486 and PLX3397 will be considered too toxic and dosing will be reconfigured.

PLX3397 dose de-escalation will be in decrements of 200 mg per day. Examples of these dose reductions are provided in [Table 21](#).

Table 21: PLX3397 Examples of Dose Reductions for the 600 mg Daily Dosing Cohorts

Dose Level	When
600 mg	Starting dose
400 mg	1 st dose reduction
200 mg	2 nd dose reduction
Off study	3 rd dose reduction required

Combination with sunitinib: If ≥ 2 of the first 6 patients who receive the first dose level in Part 2e experience a protocol-defined DLT, the administration of PLX9486 and sunitinib will be considered too toxic and dosing will be reconfigured as follows:

- Hold sunitinib for \geq Grade 3 drug related AEs
 - First occurrence:
 - Hold drug until AE \leq Grade 1 for non-hematologic events or AE \leq Grade 2 for hematologic events. Resume at same dose level if at 37.5 mg dose.
 - For Grade 3 treatment-related AE, dose reduce to 25 mg if at 37.5 mg or resume at reduced dose of 25 mg.

- For Grade 4 treatment-related AE, if at 25 mg dose level, hold sunitinib until AE \leq Grade 1 for non-hematologic events or AE \leq Grade 2 for hematologic events, then resume at 25 mg dose level or discontinue sunitinib
- Second occurrence:
 - Hold sunitinib until AE \leq Grade 1 for non-hematologic events or AE \leq Grade 2 for hematologic events. If at 37.5 mg, dose reduce to 25 mg, and if at 25 mg, discontinue sunitinib

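### Above 6 evaluable patients, the Part 1 escalation rules contradict each other: 2 DLTs in 7 or 8 stops escalation under Section 9.2.1.1 but escalates under Section 9.2.2

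*Protocol*

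**What the plan says.** **Part 1.** Section 9.2.1.1 and the synopsis continue escalation unless 2 or more DLTs occur "of at least 6 patients (i.e., 33%) in one cohort within the first 28 days". This is a count, and it sets a minimum cohort size but no maximum.

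**General rules.** The condition in Section 9.2.2 is "If less than one-third of evaluable patients in a given cohort experiences a DLT". When it is met, the section directs escalation to the next level. The next bullet calls a dose intolerable at one-third or more. The worked examples, marked as examples, go no further than 6 patients. The MTD bullet is written only for 0 or 1 DLT in 6.

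**Cohort size.** After 1 DLT in the first 3, Section 9.2.2 says "at least 3 additional patients will be enrolled in that cohort", whereas Section 9.2.1.1 says "an additional 3 patients will be treated at that dose". For the combination parts, Section 9.2.1.2 adds: "Dose adjustments may also include increasing the number of patients at a given dose level".

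**Parts 2b and 2e.** Section 9.2.1.2 stops escalation at 2 or more DLTs "of 6 patients in one cohort within the first 28 days of continuous dosing". Its separate trigger for introducing a lower dose is 2 or more in 6 or more patients, glossed as 33% or above. Section 9.2.4 declares the combination too toxic if 2 or more "of the first 6 patients who receive the first dose level in Part 2b experience a protocol-defined DLT", with a parallel sentence for Part 2e. Both are limited to the first dose level.

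**Review.** If 2 or more patients in a cohort have related Grade 2 or higher toxicity, Section 9.2.2 says "the study committee will determine the dose escalation increment after review of the safety, PK, and PD data".

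**The concern.** A count of 2 and a proportion of one-third are the same boundary only at 6 patients. Above that they separate, and the protocol allows cohorts above 6 without saying which boundary governs.

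The situation is foreseeable. Table 10 shows 7 patients enrolled at 1000 mg QD and 7 at 500 mg BID in Part 1. The Part 2b fed cohort has 7 patients in the text of Section 5.5.1.2 and 8 in Table 12.

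Establishing the MTD/RP2D (Part 1) or the RP2D (Parts 2b and 2e) is a primary endpoint. Section 14.4 states that there is no DSMC, and the Study Committee of Section 10.1.1 consists of sponsor staff and investigators. A written rule that gives two answers leaves the choice of boundary to be made after the DLTs are known.

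**Working it through.** **1. Reproduce the printed table.** Let p be the true DLT rate and q = 1 − p. The standard 3+3 escalates on 0 of 3, or on 1 of 3 followed by 0 of 3:

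P(escalate) = q³ + 3pq² × q³

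At p = 10% to 70% this gives 0.906, 0.709, 0.494, 0.309, 0.172, 0.082 and 0.032. Tables 27, 29 and 30 print 0.91, 0.71, 0.49, 0.31, 0.17, 0.08 and 0.03. They are correct for the 3 or 6 subjects they describe.

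**2. Compare the two boundaries.**

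| DLTs / evaluable | Proportion | Count rule (Section 9.2.1.1) | One-third rule (Section 9.2.2) |
|---|---|---|---|
| 2 of 6 | 33.3% | stop | stop |
| 2 of 7 | 28.6% | stop | escalate |
| 2 of 8 | 25.0% | stop | escalate |

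The 33% gloss in Section 9.2.1.1 fits 6 patients only. It shows what the author had in mind, but it does not limit the rule to 6.

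**3. Illustrate the size.** Assume that a cohort with 1 DLT in 3 is expanded to 7 evaluable patients, which the protocol allows but does not plan, and that the rule is applied before any committee judgement.

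- Count rule (at most 1 DLT in 7): q³ + 3pq² × q⁴. At p = 0.3: 0.343 + 0.441 × 0.2401 = 0.449.
- One-third rule, with 2 DLTs in the first 6 stopping escalation first. A cohort with 1 of 6 then escalates whatever happens in patient 7, so the formula is that of step 1. At p = 0.3: 0.343 + 0.441 × 0.343 = 0.494.
- One-third rule, all 7 read out together (at most 2 DLTs): q³ + 3pq² × (q⁴ + 4pq³). At p = 0.3: 0.343 + 0.441 × (0.2401 + 0.4116) = 0.630.

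| True DLT rate | Count rule | One-third, 2-of-6 stop first | One-third, all 7 together |
|---|---|---|---|
| 20% | 0.669 | 0.709 | 0.827 |
| 30% | 0.449 | 0.494 | 0.630 |
| 40% | 0.272 | 0.309 | 0.421 |

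The difference from the count rule is about 0.04 to 0.05 in the first case and 0.15 to 0.18 in the second.

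**4. Eight evaluable patients, p = 0.3.**

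- Count rule: 0.343 + 0.441 × 0.7⁵ = 0.417.
- One-third rule, 2-of-6 stop first. At most 1 DLT is allowed in the last two patients, because 3 of 8 exceeds one-third: 0.343 + 0.441 × 0.343 × (1 − 0.09) = 0.481.
- One-third rule, all 8 together: 0.343 + 0.441 × (0.16807 + 5 × 0.3 × 0.2401) = 0.576.

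**The case against.** The best defence is that the design plainly means 3 or 6. Every example in Section 9.2.2, the MTD definition, the stopping rule in the synopsis and the three probability tables use those sizes. When patients are added for reasons other than toxicity, Sections 9.2.1.1 and 9.2.1.2 let the decision follow once the first 3 clear the DLT window. Escalation also needs sponsor and investigator review, and adequate safety and tolerability at the lower dose. The planned path applies in the absence of related Grade 2 or higher toxicity, so two DLTs would already put a cohort under review. Escalation at 2 of 7 is therefore not automatic in any part.

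That limits the practical risk but does not remove the contradiction. The examples are illustrative, and the operative test in Section 9.2.2 is a proportion of evaluable patients. The review bullet sets the increment and does not choose between the boundaries.

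Three stronger readings are tempting, and the documents do not support them:

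- A reader might infer that one-third is the only boundary left in Parts 2b and 2e above 6 patients. The lower-dose trigger there also covers larger cohorts, and the safety-and-tolerability condition still applies. The text is ambiguous, not unbounded.
- A reader might take 0.15 to 0.18 as the size of the problem. That needs all 7 patients to be read out together. With the 2-of-6 stop applied as patients become evaluable, the gap is about 0.04 to 0.05.
- A reader might infer that the selected RP2D is in doubt. Part 1 is complete, and the synopsis reports a single DLT to date. The counts of 7 and 8 are enrolled, and Section 9.3 replaces non-evaluable patients, so the number evaluable may be 6 or fewer.

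**Conclusion.** The contradiction is real and minor. In Part 1, 2 DLTs in 7 or 8 evaluable patients stops escalation under Section 9.2.1.1 and the synopsis, and escalates under Section 9.2.2. Parts 2b and 2e have a related ambiguity, because the escalation stop, the lower-dose trigger and Section 9.2.2 use three different wordings. No text ranks them.

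In the 7-patient illustration the choice of rule moves the probability of escalating by about 0.04 to 0.05 at true DLT rates of 20% to 40% if the 2-of-6 stop comes first, and by 0.15 to 0.18 only if all 7 are read out at once. Both figures rest on the assumed expansion to 7 evaluable patients and on applying the rule without committee judgement. The defect is latent: no decision already taken is shown to depend on it, and the printed tables are not in error.

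**What to change.** In Section 9.2.2, replace the one-third test with one count boundary for Parts 1, 2b and 2e:

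- Escalate on 0 DLTs in 3, or on at most 1 DLT in 6 evaluable patients.
- Stop escalation at 2 or more DLTs at a dose level, including any DLT in patients beyond the sixth who are evaluable before the escalation decision.

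In the same section, make the expansion after 1 DLT in 3 exactly 3 further patients, as Section 9.2.1.1 has it. Align the escalation-stop wording in Section 9.2.1.2 and the synopsis.

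Deciding on the first 6 evaluable patients alone would also remove the conflict and would match the tables. It would, however, drop the stop that Part 1 now has for a second DLT in patient 7 or 8, so the count boundary is the safer choice.

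The cost is a few lines of text, carried through a protocol change with the IRB/IEC approval that Section 14.8 requires. No patients are added, and Tables 27, 29 and 30 stay as they are for 3 or 6 subjects. The downside is that cohorts reaching 7 or 8 evaluable patients escalate slightly less often than the tables show: 0.449 or 0.417 against 0.494 at a true DLT rate of 30%.

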9.2.3 Dose De-escalation for PLX9486

For patients receiving PLX9486 (single agent or in combination), dose de-escalation will be in decrements 100 mg per dose for a BID dosing schedule or 200 mg per dose for a QD dosing schedule. Examples of these dose reductions are provided in [Table 19](#) and [Table 20](#).

Table 19: PLX9486 Examples of Dose Reductions for the 500 mg BID Dosing Cohorts

Dose Level	When
500 mg BID	Starting dose
400 mg BID	1 st dose reduction
300 mg BID	2 nd dose reduction
200 mg BID	3 rd dose reduction
Off study	4 th dose reduction required

BID = twice daily

Table 20: PLX9486 Examples of Dose Reductions for the 1000 QD Dosing Cohorts

Dose Level	When
1000 mg QD	Starting dose
800 mg QD	1 st dose reduction
600 mg QD	2 nd dose reduction
400 mg QD	3 rd dose reduction
Off study	4 th dose reduction required

QD = once daily

Dose reductions should be discussed with the Sponsor's Medical Monitor. Please refer to [Section 9.4](#) for further instructions.

9.2.4 Dose De-escalation for PLX9486 combinations

Combination with PLX3397: If ≥ 2 of the first 6 patients who receive the first dose level in Part 2b experience a protocol-defined DLT, the administration of PLX9486 and PLX3397 will be considered too toxic and dosing will be reconfigured.

PLX3397 dose de-escalation will be in decrements of 200 mg per day. Examples of these dose reductions are provided in [Table 21](#).

Table 21: PLX3397 Examples of Dose Reductions for the 600 mg Daily Dosing Cohorts

Dose Level	When
600 mg	Starting dose
400 mg	1 st dose reduction
200 mg	2 nd dose reduction
Off study	3 rd dose reduction required

Combination with sunitinib: If ≥ 2 of the first 6 patients who receive the first dose level in Part 2e experience a protocol-defined DLT, the administration of PLX9486 and sunitinib will be considered too toxic and dosing will be reconfigured as follows:

- Hold sunitinib for \geq Grade 3 drug related AEs
 - First occurrence:
 - Hold drug until AE \leq Grade 1 for non-hematologic events or AE \leq Grade 2 for hematologic events. Resume at same dose level if at 37.5 mg dose.
 - For Grade 3 treatment-related AE, dose reduce to 25 mg if at 37.5 mg or resume at reduced dose of 25 mg.

- For Grade 4 treatment-related AE, if at 25 mg dose level, hold sunitinib until AE \leq Grade 1 for non-hematologic events or AE \leq Grade 2 for hematologic events, then resume at 25 mg dose level or discontinue sunitinib
- Second occurrence:
 - Hold sunitinib until AE \leq Grade 1 for non-hematologic events or AE \leq Grade 2 for hematologic events. If at 37.5 mg, dose reduce to 25 mg, and if at 25 mg, discontinue sunitinib

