Further dose escalation and reduction in smaller increments may be undertaken at any time based upon emerging safety, PK, and PD data. Dose adjustments may also include increasing the number of subjects at a given dose level as a result of the review of safety and PK data by the Sponsor and investigators. In addition, alternative dosing schedules may be explored, such as continuous dosing followed by a rest period, staggered dosing of the agents, etc., depending on the safety, PK, or PD-generated data.

If a DLT is observed in one patient at a given cohort, an additional 3 patients will be enrolled into the cohort. If DLT is observed in ≥ 2 of at least 6 patients (i.e., $\geq 33\%$) at a dose level, then a lower dose level of PLX9486 may be introduced to the combination regimen. If no DLT is observed, the recommended dose for further evaluation may be established based on toxicity, PK, and convenience of dosing in approximately 3 to 6 patients treated at that dose. Dose escalation will only be permitted if adequate safety and tolerability have been demonstrated at the previous lower dose for 28 days.

In addition, if the Study Committee ([Section 10.1.1](#)) determines that, in the absence of DLTs, enrollment of additional patients is required in order to better understand PK, safety, or pharmacodynamic markers in specific patient types (e.g., patients with exon 17 mutations), an additional 3 patients may be undertaken at one or more of the dose levels already studied or currently being studied. Alternatively, a split dosing schedule (e.g., BID) may be studied at the current dose level under study or previously studied daily dose levels. Should more than 3 patients be accrued to a dose level for reasons other than DLT/toxicity, the decision to escalate further may be made after the first 3 patients clear the DLT window period after review of the available data by the Study Committee.

Once the safety and tolerability of a dose level of PLX9486 in combination with sunitinib have been established by 3 to 6 patients treated for 28 days (one cycle), intra-patient dose escalation to the next dose level may be permitted for patients at lower dose levels who have not experienced a Grade 3 or higher treatment-related toxicity that has not resolved.

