Detailed medical history and physical examination seeking new abnormalities.	Evaluate abnormalities found.
Full serological evaluation for hepatitis A, B, C, and E (IgG and IgM). Check for autoimmune hepatitis with serological laboratory studies.	If viral hepatitis or autoimmune hepatitis suggested, have patient evaluated by hepatologist.
Liver ultrasound performed to evaluate liver and biliary tree.	Evaluate any abnormalities found.
Check history for exposure to chemical agents.	Remove chemical exposure and have patient seen by hepatologist.
Obtain hepatology consult if liver function continues to rise beyond 14 d.	Contact Medical Monitor.
We request that cases be discussed with the Medical Monitor as defined in the protocol whenever investigational product is being held for liver function test abnormality.	

Ig = Immunoglobulin; INR = international normalized ratio; OTC = over-the-counter

For suspected cases of cholestatic liver injury (e.g., aminotransferase increase concurrent with hyperbilirubinemia, or liver biopsy suggesting cholestasis and/or ductopenia), patients will be followed to assess long-term outcome. Additional diagnostic and follow-up procedures might be implemented as appropriate to fully assess the event.

Sunitinib Dose Modification Guidelines:

For all sunitinib drug modifications, see [Section 9.2.4](#). For further guidance, consult the package insert.

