10.3 Treatment Group Assignments

This is an open-label, sequential dose-escalation study with extension cohorts. The initial dose level of PLX9486 will be 250 mg/day. Thereafter, dose-escalation groups will occur as described in [Section 9.2.1](#). Extension cohorts will be enrolled in parallel at the RP2D according to inclusion and exclusion criteria ([Section 8.1](#) and [Section 8.2](#)). The initial dose of PLX3397 will be 600 mg/day administered BID. Thereafter, dose escalation groups will occur as described in [Section 9.2.1.2](#). For the combination cohort with sunitinib the initial sunitinib dose will be 25 mg/day. Further details may be found in [Section 9.2.1.2](#).

10.4 Withdrawal of Patients from Drug Treatment or from the Study and Patient Replacement

The Plexxikon Medical Monitor will monitor safety data throughout the course of the study. The Medical Monitor will review SAEs within timeframes mandated by company procedures and will review trends, laboratory data, and AEs at periodic intervals and provide for interim safety analyses if appropriate.

The reasons a patient may discontinue or be withdrawn from the study include, but are not limited to, adverse event, clinically significant disease progression, patient request, investigator decision, protocol violation, patient noncompliance, and study termination by the Sponsor or institutional review board (IRB)/independent ethics committee (IEC). When a patient discontinues or is withdrawn, the investigator will notify the Sponsor and should perform the procedures indicated in the End of Study column in the Schedule of Events within 30 days after discontinuation of study drug and before initiation of any new anti-cancer therapy. Follow-up information will be obtained for patients who discontinue their participation in or are withdrawn from the study.

Patients withdrawn from the study for reasons other than toxicity or clinically significant disease progression (e.g., protocol violation or noncompliance) may be replaced at the discretion of the medical monitor and the investigator. Study drug administration may be discontinued due to an adverse event or at the discretion of the investigator.

The consequence of withdrawal of consent by a patient will be that no new information will be collected from that patient and added to the existing data or any database. However, every effort will be made to follow all patients for safety.

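### Section 9.2.4 gives two incompatible sunitinib doses after a first drug-related Grade 3 event at 37.5 mg, and has no Grade 4 line for that dose

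*Protocol*

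**What the plan says.** Section 9.2.4 tells sites to hold sunitinib for drug-related events of Grade 3 or higher and then lists what follows.

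- First occurrence, general line: hold until recovery, then "Resume at same dose level if at 37.5 mg dose".
- First occurrence, Grade 3 line: "dose reduce to 25 mg if at 37.5 mg or resume at reduced dose of 25 mg".
- First occurrence, Grade 4 line: "For Grade 4 treatment-related AE, if at 25 mg dose level, hold sunitinib until" recovery, then resume at 25 mg or discontinue. The 37.5 mg dose is not named.
- Second occurrence: hold until recovery, then "If at 37.5 mg, dose reduce to 25 mg, and if at 25 mg, discontinue sunitinib".

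Section 9.4 sends the reader back to this list: "For all sunitinib drug modifications, see" Section 9.2.4. It also points to the package insert, calls its parameters guidance that does not override clinical judgment, and asks for consultation with the Medical Monitor. In Part 2e, if one drug is permanently stopped, both are, and the patient leaves the study.

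The 37.5 mg dose is used in Cohort 3 (Table 18). It can also be reached by patients who started lower, because "intra-patient dose escalation to the next dose level may be permitted for patients at lower dose levels" (Section 9.2.1.2).

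**The concern.** Two lines under the same sub-heading, for the same grade, dose and occurrence, give different doses. They are not offered as alternatives, and no criterion is given for choosing. Two sites following the text could treat identical patients differently after severe toxicity, one resuming 37.5 mg and the other reducing to 25 mg. The first choice also sets the next step, because the second-occurrence action depends on the dose the patient is then taking. Safety and tolerability are a primary endpoint of Part 2e, and the Synopsis says that patients were still being treated there at the time of this amendment.

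**Working it through.** The protocol states no figure here to reproduce. The check maps each combination of grade, dose and occurrence to its instruction, then looks for text elsewhere that would settle a conflict.

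**Action map, Section 9.2.4 (after recovery)**

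| Occurrence | Grade | Dose | Instruction |
|---|---|---|---|
| First | 3 | 37.5 mg | General line: 37.5 mg. Grade 3 line: 25 mg. Conflict. |
| First | 4 | 37.5 mg | No own line. General line by default: 37.5 mg. |
| First | 3 | 25 mg | 25 mg |
| First | 4 | 25 mg | 25 mg or discontinue |
| Second | 3 or 4 | 37.5 mg | 25 mg |
| Second | 3 or 4 | 25 mg | Discontinue |

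Of the four first-occurrence cells, one is contradictory and one has no line of its own.

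**Can either line be read as governing?**

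- If the Grade 3 line overrides, the 37.5 mg sentence in the general line is left for Grade 4 only. Grade 4 then resumes at full dose while Grade 3 is reduced. The second-occurrence step from 37.5 to 25 mg would then concern only patients whose first event was Grade 4 or who were re-escalated under Section 9.2.5.
- If the general line governs, the Grade 3 instruction for 37.5 mg has no effect.

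**Does other text settle it?** Section 9.4 refers back to 9.2.4 and to the package insert. Table 22 governs PLX9486 steps, not sunitinib steps. Section 9.2.5 concerns re-escalation after a reduction. None of these says which line applies.

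**Size for one patient** (daily dosing over a 28-day cycle, hold days ignored)

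- 37.5 × 28 = 1050 mg; 25 × 28 = 700 mg.
- Difference: 1050 − 700 = 350 mg per cycle; 350 / 1050 = 33%.

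**Two successive Grade 3 events, no re-escalation**

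- General line followed: 37.5 → 37.5 → 25 mg.
- Grade 3 line followed: 37.5 → 25 → sunitinib discontinued, and through Section 9.4 both drugs stop and the patient goes off study.

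**The case against.** **The specific line overrides the general one.** This ordinary reading would remove the contradiction, but at the price of milder handling for Grade 4 than for Grade 3. Table 22 limits that price. For other Grade 4 toxicities related to PLX9486, it reduces PLX9486 if recovery takes under 5 days and stops it permanently if symptoms last 5 days or more, or recur. A permanent stop then ends both drugs. This stands, so the Grade 4 gap is narrower than the list alone suggests. It remains for events attributed to sunitinib alone and for uncomplicated Grade 4 neutropenia or non-bleeding thrombocytopenia, where Table 22 itself allows same-dose resumption of PLX9486 after recovery within 7 days.

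**Grade 4 at 37.5 mg has no instruction at all.** A reader might infer this. The text does not support it, because the general line covers Grade 3 or higher. The defect is a missing specific line with a poor default.

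**The 37.5 mg lines apply to nobody.** A reader might also infer this, because the list is introduced as the response when two or more "of the first 6 patients who receive the first dose level in Part 2e experience a protocol-defined DLT", and Section 10.3 says "For the combination cohort with sunitinib the initial sunitinib dose will be 25 mg/day". Section 9.4 refuses that reading by making the list the rule for all sunitinib modifications. The misplaced lead-in is editorial.

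**Guidance status and Medical Monitor consultation.** These soften the effect in practice, as may the package insert, which is not before us. They leave each case to be settled ad hoc and do not say which line governs.

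**A reduction rule collides with Section 9.3.** Reductions in the DLT window are barred for patients counted in escalation decisions. Some drug-related Grade 3 events, such as fatigue resolving to Grade 2 or lower within 14 days, are not DLTs. A blanket reduction would therefore order what Section 9.3 forbids. This stands, and the fix has to deal with it.

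**Conclusion.** The contradiction is real for a first drug-related Grade 3 event at 37.5 mg, and Grade 4 at that dose lacks its own line. The choice decides 37.5 or 25 mg/day (33%) and, after a second event, 25 mg or the end of both drugs. The second contrast assumes no re-escalation under Section 9.2.5 and a second event on both paths, although a patient already reduced may be less likely to have one.

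Two larger claims are not supported. A reader might infer that the dose-finding result is affected, but DLT counts, the MTD rule and Table 30 do not depend on these lines, and toxicities outside the DLT window are only taken into account for the RP2D. A reader might also multiply the per-cycle difference into a cumulative loss. The protocol gives neither an event rate at 37.5 mg nor a time on treatment after an event, and Section 9.2.5 allows re-escalation. That offset is partial: it needs a previous cycle at the reduced dose with no treatment-related non-hematologic event and no Grade 2 or higher hematologic event, and the commonest PLX9486-related events are fatigue, diarrhea and nausea.

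The correction should be made: it is a safety rule that is wrong as written and cheap to repair.

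**What to change.** State one action per grade, dose and occurrence, for all Part 2e patients.

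- **Conservative default.** Delete the same-dose sentence for 37.5 mg. After recovery from a first Grade 3 event at 37.5 mg, resume at 25 mg. After a first Grade 4 event at 37.5 mg, resume at 25 mg or discontinue.
- **If the sponsor intends same-dose resumption for Grade 3.** The second-occurrence line fits that intention better. Limit it to the recovery conditions Table 22 already uses (7 days for neutropenia or non-bleeding thrombocytopenia, 5 days for other Grade 3 toxicities), and still add the Grade 4 line at 37.5 mg.
- **Cycle 1.** A patient counted for escalation who has a Grade 3 event excepted from the DLT definition is held and resumed at the same dose, with any reduction deferred until the DLT window closes. If the dose is reduced for safety, the Study Committee decides on evaluability. A patient with a DLT may continue at a lower dose under Section 9.3.
- **Second occurrence.** State that the 37.5 mg line applies to patients kept at that dose or re-escalated to it under Section 9.2.5.
- **Editorial.** End the cohort sentence once it says that dosing will be reconfigured, as the PLX3397 paragraph does, and give the patient-level list its own heading.

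The cost is one rewritten list and lead-in, with cross-references to Sections 9.2.5 and 9.3. Sample size, DLT definition, escalation rule and assessments stay as they are. The downside of the conservative default is somewhat lower sunitinib exposure after a first event, partly offset by Section 9.2.5.
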